Adapted from Clinical Therapeutics, Vol. 23, Claxton AJ, Cramer J, Pierce C. A systematic review of the associations between dose regimens and medication compliance, pgs. 1296-1310, Copyright 2001, with permission from Excerpta Medica, Inc.⁴⁴

3. Study design
 1. Single-center, open-label, randomized comparative pilot trial.
 2. There will be 20 subjects in each arm, with a total study size of 40 subjects.
2. Allocation: Four random permuted-blocks of ten with equal arm allocation ratio will be used. Since no other stratification criteria are considered, larger block sizes will be appropriate. In each block, ten random numbers will be generated using SAS 9.4 with a range from zero to ninety nine. Even numbers will be assigned the intervention arm and odd numbers will be assigned the standard of care with resulting 1:1 allocation.
3. Intervention Model: Parallel assignment
4. Masking: This will be an open-label study as masking is not feasible given we are comparing twice-a-day to once-a-day regimen and its effect on adherence.
5. Selection and enrollment of subjects
 1. Inclusion criteria
 1. Male or female adult (≥ 18 years old) with a history of solitary kidney transplant within 3 months (± 2 months) of transplant.
 2. Patients must be capable of understanding the purposes and risks of the study and have the ability to give written informed consent and be willing to participate and comply with the study.
 3. Women of childbearing potential and sexually active males must be willing to use contraception, as indicated in Section 6 of the protocol. Subjects who are not of reproductive potential (status post bilateral tubal ligation, bilateral oophorectomy, hysterectomy, or vasectomy), not sexually active, whose current partner(s) is not of reproductive potential, or whose sexual activity is exclusively homosexual are eligible without requiring the use of contraception.
 2. Exclusion criteria
 1. Patients will be excluded if they are pregnant or nursing females or males with a pregnant female partner
 2. Recipient of multiple organ transplant
 3. Recipient of a non-renal organ
 4. Proteinuria > 800 mg/24 hour
 5. eGFR < 30 ml/min
 6. WBC $\leq 2k/mm^3$

7. $\text{Plt} \leq 50\text{k}/\text{mm}^3$
 8. Triglycerides $> 500 \text{ mg/dL}$
 9. HIV positive (HIV ab +)
 10. Unable to tolerate oral medications
 11. Use of another investigational product within thirty days prior to receiving study medication

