- 1.** No formal power analysis conducted since this is a pilot study. However, the sample size proposed (n=40) would be able to observe a mean difference between groups in the change of MMAS-8 scores of 2 ± 2 points (95% CI 0.73,3.27) with 87% power. Additionally, a mean difference between groups in the change in the Memphis Side Effect Scale (MSES) of 5 ± 5 points (95% CI 1.83,8.17) would have 87% power in the current sample size. Given the average MSES score of 25 points in kidney transplant patients within 2 years of transplant, this appears to be a feasible outcome (11). In order to demonstrate noninferiority in treatment failure, it would require 400 subjects (200 in each group) to have 80% power, estimating a treatment failure rate of 20% and an acceptable difference of 10%. We expect that 70% of those approached meeting study inclusion/exclusion criteria will agree to participate and that 85% of those that consent and are enrolled in the study will complete all visits. If the 95% CIs for the actual enrollment and completion proportions are outside of these thresholds, then feasibility will not be met. If the 95% CIs encompass these expected values, then feasibility will be met.

3. Missing data and imputation methods

- 1.** Under the intention-to-treat principle, all subjects are included in the analysis. Extensive efforts will be made to keep all missing data to a minimum and minimize loss to follow-up (LTFU). However, it is likely that some missing data may occur.

11. Human subjects

1. Institutional review board (IRB) review and informed consent

- 1.** This protocol, the ICF, and any subsequent modifications must be reviewed and approved by the IRB. A signed and dated ICF must be obtained from the subject as defined in 21CFR50.3. The ICF must also be signed and dated by a member of the study staff qualified to be delegated the authority to obtain informed consent. A copy of the ICF must be given to the subject and the consent process must be documented in the subject's medical record. The PI or delegated sub-Investigator is responsible for ensuring that informed consent is obtained from each patient prior to conducting any study-related activities.

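### The even/odd rule in the allocation section is simple randomization and does not produce the balanced blocks of ten, or the 20 per arm, that the section promises

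*Combined protocol and SAP*

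**What the plan says.** Section 3 (Study design) fixes the arm sizes: "There will be 20 subjects in each arm, with a total study size of 40 subjects". Its Allocation item names the method: "Four random permuted-blocks of ten with equal arm allocation ratio will be used". Equal allocation in blocks of ten means five per arm in every block, although the ratio 5:5 is not printed.

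The same item then gives the mechanism: "In each block, ten random numbers will be generated using SAS 9.4 with a range from zero to ninety nine", followed by "Even numbers will be assigned the intervention arm and odd numbers will be assigned the standard of care with resulting 1:1 allocation". On block length it adds "Since no other stratification criteria are considered, larger block sizes will be appropriate".

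No other section adds a balancing step. The enrollment procedures and the timing-of-evaluation text say only that eligible subjects are randomized, and when. Section 10 states 87% power for the primary outcome at n=40.

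**The concern.** A permuted block is balanced because a fixed set of labels is shuffled. Assigning each subject by the parity of a random number is a coin flip for each subject, and the block boundaries then do nothing. The section presents 1:1 as the result of the parity rule, but the rule does not give that result in any block or at 40 subjects.

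Two programmers could therefore work from the same text and build different designs, one following the method's name and the other its procedure. At stake are the reproducibility of the allocation and the stated arm sizes. Validity of the comparison is not at stake, because simple randomization is unbiased.

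**Working it through.** **Inputs.** From Section 3: 40 subjects, four blocks of ten, integers 0 to 99, even to intervention, odd to control. That range holds 50 even and 50 odd integers, so P(even) = 0.5 if draws are uniform. The text does not say whether numbers may repeat, so three variants were run. From Section 10: difference 2, SD 2, n=40, 87% power, 85% completion. No test or alpha is named; a two-sided 5% two-sample t-test is assumed.

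**The plan's own power figure.** With standardized difference 2/2 = 1, the noncentrality is √(n₁n₂/(n₁+n₂)). At 20:20 this is √10 = 3.162 with 38 df, giving 86.9%. The stated 87% is reproduced, so it corresponds to equal arms.

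**Balance under the literal rule.**

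- One block, with replacement: C(10,5)/2¹⁰ = 252/1024 = 24.6%. All four: 0.2461⁴ = 0.37%.
- One block, no repeats within it: C(50,5)²/C(100,10) = 25.9%. All four: 0.2593⁴ = 0.45%.
- Total of exactly 20:20, with replacement: C(40,20)/2⁴⁰ = 12.5%.
- Mean absolute difference in arm sizes, with replacement: 40 × 0.1254 = 5.0 subjects.

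| Sampling | Exactly 20:20 | 24:16 or worse |
|---|---|---|
| With replacement | 12.5% | 26.8% |
| No repeats within a block | 13.2% | 24.5% |
| No repeats across all 40 | 16.2% | 15.3% |

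No reading of the sampling restores the claimed balance.

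**Cost in power.**

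| Split | Noncentrality | Power |
|---|---|---|
| 20:20 | 3.162 | 86.9% |
| 24:16 | √9.6 = 3.098 | 85.5% |
| 25:15 | √9.375 = 3.062 | 84.7% |
| 14:26 | √9.1 = 3.017 | 83.6% |
| Averaged over Binomial(40, 0.5) | – | 86.0% |

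The average loss is 86.9 − 86.0 = 0.9 points. For scale, Section 10 expects that "85% of those that consent and are enrolled in the study will complete all visits". That is 0.85 × 40 = 34 subjects; if they split 17:17, the noncentrality is √8.5 = 2.915 with 32 df and power is 80.7%. Expected attrition costs more than the allocation rule.

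**Predictability once blocks are truly balanced.** When one label is used up, the rest of the block is determined. The number of determined assignments is the length of the final run of one label. Over all 252 sequences the mean is 1 + 4/9 + 12/72 + 24/504 + 24/3024 = 1.67, and the chance of two or more is 4/9 = 44%.

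**The case against.** The strongest reply is that the section should be read as a whole. It first names permuted blocks with equal allocation, a method defined by fixed balance, and parity may be only the labeling device inside that constraint. A programmer who drew a 7:3 block would see that it breaks the opening sentence. On this view the text is incomplete, not contradictory.

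The intent is plausible and is granted. But the parity sentence offers 1:1 as the outcome of parity, and no redraw, cap, ranking or five-and-five condition is written. As it stands, the stated procedure does not yield its stated result.

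Several other points stand:

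- The effect is small, and the trial is a pilot for which the protocol disclaims a formal power analysis. The feasibility criteria do not depend on arm balance.
- The low probabilities of exact balance measure the gap between text and claim. They do not measure harm, and they depend on the literal reading.
- Predictability at the end of a block comes from the fixed block of ten that the protocol already declares, not from the parity rule. It matters here only because the correction makes that block structure real.
- Confirming eligibility before randomization is already set out in the enrollment and timing sections. Only concealment of the list is unstated.

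**Conclusion.** The point holds: the parity rule does not guarantee 5:5 blocks or 20 per arm. Followed literally, it leaves at least one block unbalanced with probability above 99% and misses 20:20 with probability between 83.8% and 87.5%, depending on how repeats are handled (100% less 16.2% or 12.5%).

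The consequence is modest. Allocation stays unbiased, type I error is unaffected, and mean power falls by 0.9 points with replacement, on the assumption of a two-sided 5% t-test with difference 2 and SD 2. The balance figures assume uniform draws. The finding concerns the text only, since the documents do not show how the list was generated. It should be fixed because the protocol ought to describe one reproducible method that gives the arm sizes it states.

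**What to change.** Replace the parity sentence with a true permutation, for example: within each block of ten, five intervention and five control labels will be placed in random order (SAS PROC PLAN). Two alternatives are equivalent in effect:

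- Rank ten continuous random numbers and give the five lowest to the intervention. Integers 0 to 99 drawn with replacement should not be ranked this way: in simulation, a tie at the fifth and sixth places occurs in about 4.9% of blocks, or 18% for at least one of four.
- If parity was intended, state that each block contains exactly five even and five odd numbers.

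Each gives 5:5 in every completed block and 20:20 at 40.

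Because this is a "Single-center, open-label, randomized comparative pilot trial" with a disclosed block length, staff who track earlier assignments can predict the last ones in a block. Add a sentence that the list is concealed from enrolling staff, with each assignment released only after the eligibility confirmation already described.

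The cost is one or two sentences and a few lines of SAS, with no added patients, visits or budget. The price is the end-of-block predictability, which concealment reduces.

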Protocol Version 4.0
11May2017

Title:

Once-daily regimen with Envarsus® to optimize immunosuppression management and adherence in kidney transplant recipients

Institution:

Medical University of South Carolina

Principal Investigator:

[name]
Office: [contact]
[contact]
Email: [contact]

Sub-Investigators:

[name]
Office: [contact]
[contact]
Email: [contact]

[name]
Office: [contact]
[contact]

[name] [name]
Office: [contact]
Email: [contact]

1. Study Objectives

1. Primary objective

1. Estimate change from baseline to six months in adherence superiority measure by MMAS-8 in patients converted to a once-daily immunosuppressant regimen of Envarsus[®], everolimus, and prednisone versus patients converted to a twice-daily regimen of Envarsus[®] (once daily), MMF (twice daily), and prednisone (once daily).

2. Secondary objectives

1. Estimate the composite of treatment failure rate, defined as acute allograft rejection with a Banff grade 1A or higher, graft loss, or death at six months post-conversion, in patients converted to a once-daily immunosuppressant regimen of Envarsus[®], everolimus, and prednisone versus patients converted to a twice-daily regimen of Envarsus[®], MMF, and prednisone.

3. Outcomes 3.3.2 through 3.3.11 are considered exploratory

1. Examine subject specific change of the Memphis Medication Side Effect Scale (Appendix B2, 12) at the time of the conversion versus six months post-conversion, compared between the two arms (Appendix B2).
2. Examine subject specific change in quality of life, using the SF-36 (Appendix B3) at the time of conversion versus six months post-conversion, compared between the two arms.
3. Measure and compare time-to-event analysis of secondary objective between the two arms
 1. Patient death (time to event analysis)
 2. Biopsy proven acute rejection (Banff 1a or higher, time to event analysis)
 3. Graft loss (time to event analysis)
4. Examine the medication possession ratio (MPR) of adjunctive immunosuppressants (Everolimus or mycophenolate) during follow up between the two arms
 1. Compare the prevalence of patients with MPR >80%
5. Compare rates of adverse events and severe adverse events between the two arms
6. Perform exploratory analysis of subclinical rejection and IF/TA in patients with one year protocol biopsies as compared to three month protocol biopsies between the two arms

2. Background

1. Rationale

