 1. For the first three months (± 2 months) post-transplant, the pool of patients from which subject of this study will be recruited will receive the current standard of care. Standard of care is described as a regimen of tacrolimus IR BID (5-12ng/mL) + MMF 1g BID + prednisone QD Three months (± 2 months) post-transplant and at the time of recruitment, they are randomized to one of the two arms to either receive a complete once-a-day regimen or to receive twice-daily regimen.
 2. Post-randomization, subjects will be converted to one of the two arms, as shown below, and followed for a total period of six months (primary endpoint), or until a terminal end point is reached.
 1. Arm 1: Control-- twice-daily regimen of Envarsus QD (5 - 12ng/mL) + MMF (goal dose 1g BID) + prednisone QD for 6 months

2. Arm 2: Intervention-- once-a-day regimen of Envarsus QD (2- 5ng/mL) + everolimus QD (3-8ng/mL) + prednisone QD for 6 months
 1. Envarsus will be supplied for both Arms from Veloxis Pharmaceuticals
2. Adherence assessment
 1. Adherence to the study intervention will be assessed at all study visits noted on the Schedule of Evaluations (Section 5.1), using the eight point Morisky Medication Adherence Scale (MMAS-8) (17).
5. Clinical and laboratory evaluations
 1. Schedule of evaluations

Data Collection Schedule

Report Form		Baseline	Days Post-Conversion							
			7±2	14±3	30±5	60±7	90±7	120±7	150±7	180±7
Informed Consent Obtained		X								
Randomization		X								
Review of Inclusion and Exclusion Criteria		X								
Medical History		X								
Kidney Transplant Recipient		X								
Vital Signs		X					X			X
Review of Medications and Dosing		X								
Clinical assessment*	Adverse events, dosage and adherence, rejection, infection, hospitalization				X	X	X	X	X	X
	MMAS-8, MMSE Scale, and SF36 (15,16,20)	X								X
Laboratory Assessments	CBC and Chem-7 ¹	X*	O	O	O	O	O	O	O	X*
	Everolimus CO ₂		X*	X*	X*	X*	X	X*	X*	X*
	Tacrolimus CO ₂	X*	X*	X*	X*	X*	X	X*	X*	X*
End of Study										X

X=required; O=optional: data will be collected if performed as standard of care; *=not current standard of care

Footnotes:

1. Includes sodium, potassium, chloride, CO₂, BUN, SrCr, glucose, calcium, WBC, HgB, Hct, platelets
2. Tacrolimus and Everolimus concentrations will be 12- or 24-hour levels , drawn in the morning of each assessment

2. Timing of evaluation
 1. Pre-Randomization Evaluations
Baseline

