Evaluations listed under the baseline visit may be performed up to 14 days prior to randomization. Once the subject has been successfully screened and accepted for randomization, randomization must be completed within 48 hours.

2. Intervention and Evaluations

Once the subject has been successfully randomized, the patients will be directed to the hospital pharmacy to pick up study medications. Study evaluations must take place within the time window indicated on the Schedule of Evaluations (Section 5.1)

3. Clinical and Laboratory Assessments:

1. Laboratory evaluations will be performed at certified laboratories according to the study schedule. Required tests are specified in the Schedule of Evaluations (Section 5.1)
2. All subjects will undergo clinical assessment by the investigator or the investigator's designee in the manner and at the times specified in the Schedule of Evaluations (Section 5.1)
 1. Adverse events will be determined and defined according to Section 8 of the protocol
 2. Doses will be recorded of all immunosuppressants. The adjuvant immunosuppressant (mycophenolate or everolimus) will be counted and compared to the amount expected to be remaining based on the prescribed amount. An MPR will be calculated as follows: $(\text{Total Days' Supply in Period} / (\text{Last Fill Date} - \text{First Fill Date} + \text{Last Fill Days' Supply}))$
 3. Rejection and infection events will be recorded, as defined in Section 5.4)
 4. Hospitalization events will be determined by questioning the subject and review of hospital admissions in the EHR.
3. Graft function assessment will be monitored at regular intervals using the 4-variable abbreviated MDRD equation. It will be monitored at baseline and the end of the study for study outcomes and any time points dictated by standard of care follow-up in between those time points.

4. Definitions

1. Acute rejection is defined as a renal allograft biopsy showing grade 1A or greater, by the 1997 Banff Criteria and all updates since then. Biopsies will be performed when clinically warranted, based on changes in allograft function.
2. Rejection reversal is defined as return of serum creatinine to within 10% of baseline and/or histologic clearance by Banff Criteria
3. Resistant acute rejection is defined as no clinical or histologic improvement by renal biopsy within 7-10 days of initiation of treatment.

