AEs and SAEs will be reported in accordance with the FDA Guidelines for Post-Marketing Reporting of Adverse Events 21 CFR 314.80 and 21 CFR 600.80

<http://www.fda.gov/medwatch/report/regs.htm>. Any serious adverse event or a non-serious adverse event that is related to the study and unexpected will be reported to the FDA, per reporting guidelines, as soon as possible, but no later than 15 working days.. Further, all serious adverse events that are related to the study and are unexpected must be reported to The Medical University of South Carolina IRB within 10 days per The Medical University of South Carolina IRB Unanticipated Problems and Adverse Events Policy and Procedures reporting guidelines.

9. Criteria for intervention discontinuation

1. The intervention will be withheld/discontinued for AE of grade 3 or higher or if requested by the study participant.
2. Additionally, the intervention will be discontinued if the subject meets criteria for the following reasons:
 1. Pregnancy: If a woman becomes pregnant or a male's female partner becomes pregnant while on-study, the subject will be required to instruct investigators immediately.
 2. Loss of graft: Defined as death or need for retransplant. Patients will be deemed a treatment failure and the intervention will be discontinued.\

10. Statistical considerations

1. Outcomes
 1. Primary outcome- Treatment efficacy, defined difference in change from baseline to six month measure by MMAS-8 in both arms.
 2. Secondary objectives
 1. Secondary outcome- Safety outcomes of treatment failure rate, defined as acute allograft rejection with a Banff grade 1A or higher, graft loss, or death at one year post-conversion in both arms.

2. Sample size estimation for the primary outcome

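### The MPR denominator ends when the last fill runs out, so time after a subject stops refilling the adjunctive drug is never counted and early stoppers can be classed as MPR >80%

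*Combined protocol and SAP*

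**What the plan says.** Section 1 (Study Objectives) lists as exploratory: "Examine the medication possession ratio (MPR) of adjunctive immunosuppressants (Everolimus or mycophenolate) during follow up between the two arms". Beneath it stands the binary comparison, "Compare the prevalence of patients with MPR >80" per cent.

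Under Study interventions, subjects are converted and "followed for a total period of six months (primary endpoint), or until a terminal end point is reached".

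Section 5, Clinical and Laboratory Assessments, gives the rule ("An MPR will be calculated as follows"). The numerator is "Total Days' Supply in Period". The denominator is the last fill date minus the first fill date, plus "Last Fill Days' Supply". The period named in the numerator is not defined. The same item says that the adjunctive drug "will be counted and compared to the amount expected to be remaining based on the prescribed amount", but the count does not enter the formula and no rule ties it to the 80% threshold.

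Section 9 (Criteria for intervention discontinuation) allows stopping: "The intervention will be withheld/discontinued for AE of grade 3 or higher or if requested by the study participant". Section 7 returns withdrawn subjects to standard of care. The missing-data item in Section 10 keeps all subjects in the analysis under intention to treat.

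**The concern.** The objective concerns possession over follow-up, but the formula measures possession only up to the exhaustion of the last fill. It picks up gaps between refills and misses stopping altogether. No other part of the protocol extends the denominator to Day 180 or gives a rule for a subject who fills once or stops refilling.

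The primary outcome is self-reported MMAS-8 in an open-label comparison of once-daily with twice-daily dosing. MPR is the natural check on it, because no other named adherence outcome avoids self-report. A check that can score early stopping as full possession is weak.

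Stopping may also differ by arm. Standard of care contains mycophenolate but not everolimus, so a withdrawn control subject may continue the same adjunctive drug while a withdrawn intervention subject would not. The formula would not show that difference.

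**Working it through.** The protocol states no expected MPR value or MPR sample size, so there is no figure to reproduce. The check evaluates the formula directly.

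**Inputs.**
- Formula: Section 5, Clinical and Laboratory Assessments.
- Threshold of 80%: Section 1.
- Follow-up of 180 days: Study interventions and the schedule of evaluations.
- Fill length: not given. 30 days is assumed, with 90 days as a range check.

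**Algebra.** Let S be the total days' supply and G the net days of gap between successive fills. Last fill minus first fill equals the supply of all fills but the last, plus G. Adding the last fill's supply gives

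MPR = S / (S + G).

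Nothing after the last supply runs out enters G. If G = 0, MPR is 100% whatever the number or length of fills. With a single fill, G is always 0. MPR exceeds 80% whenever G is less than S/4.

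**On-time 30-day fills, then no more.** With k fills the protocol's formula gives 30k / (30(k − 1) + 30) = 100%. A fixed 180-day denominator gives 30k / 180.

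| Fills before stopping | Protocol formula | Fixed 180 days | Class at >80% changes? |
|---|---|---|---|
| 1 | 100% | 16.7% | yes |
| 2 | 100% | 33.3% | yes |
| 3 | 100% | 50.0% | yes |
| 4 | 100% | 66.7% | yes |
| 5 | 100% | 83.3% | no |
| 6 | 100% | 100% | no |

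One 90-day fill and then nothing gives 100% by the formula and 90/180 = 50% on the fixed window. Since 0.80 × 180 = 144, the class changes only if the days covered do not exceed 144.

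**Late refills, then no more.** If each refill is g days late, G = (k − 1)g and MPR = 30k / (30k + (k − 1)g).

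| Fills before stopping | g = 7 | g = 10 |
|---|---|---|
| 2 | 60/67 = 89.6% | 60/70 = 85.7% |
| 3 | 90/104 = 86.5% | 90/110 = 81.8% |
| 4 | 120/141 = 85.1% | 120/150 = 80.0% |
| 5 | 150/178 = 84.3% | 150/190 = 78.9% |

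On the fixed window, the 7-day-late subjects with 2, 3 and 4 fills have 33.3%, 50.0% and 66.7%, all still classed above 80% by the formula. With 10-day delays, four fills give exactly 80.0% and five give 78.9%; neither exceeds the threshold.

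**The case against.** Four points on the other side carry weight.

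1. **MPR is exploratory in a 40-subject pilot.** Neither the MMAS-8 outcome nor treatment failure uses it. Feasibility rests on enrolment and completion, and the examples for stopping the study are rejection, infection and graft loss. This stands and limits the importance of the point.

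2. **Other adherence information is collected.** A reader might infer that MPR is the only objective adherence measure. The protocol does not support that. It requires a drug count, a clinical assessment that covers adherence from Day 30, and everolimus and tacrolimus levels at all eight post-conversion visits. A subject who stopped everolimus would probably show in the levels. Mycophenolate has no scheduled level, so control subjects depend on the count and the visit assessment. None of these is a named outcome or feeds the >80% class, so the formula remains uncorrected.

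3. **Not every subject who stops scores 100%.** That needs a single fill or no net gap before stopping. As shown, 10-day delays can bring the score to 80% or below.

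4. **Some stopping is not non-adherence.** Refills may end because the drug was discontinued for a grade 3 or higher event, or because the subject left the study. Running every denominator to Day 180 would penalise these subjects, and more so in the everolimus arm. This stands and shapes the fix.

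**Conclusion.** The point holds as a fault in a stated formula. The denominator does not cover the follow-up period that the objective names, and nothing else in the protocol corrects it. That a single fill or a run of on-time fills scores 100% is algebra and needs no assumption about fill length. The coverage figures of 17% to 67% assume 30-day fills.

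No arm-level size can be given. Section 10 expects 85% of enrolled subjects to complete all visits, and a reader might infer that the other 15% (0.15 × 20 = 3 per arm) would be wrongly counted as above 80%. The protocol does not support that figure. Missing a visit is not the same as ceasing to refill, some non-completers will have had the drug stopped or will have withdrawn, and a stop after five monthly fills is classed the same way under either denominator. Nor do the documents establish which arm would be favoured.

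The change is worth making because it is cheap and MPR is the one named adherence outcome free of self-report. It does not threaten the primary analysis.

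**What to change.** Replace the formula with days covered in a fixed window, and define that window as the period.

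- **Start:** conversion, with credit for adjunctive drug already on hand; or the first post-conversion fill, in both arms alike. The credit matters because controls already take mycophenolate before conversion. The first-fill start avoids having to establish supply on hand at conversion.
- **End:** Day 180, or earlier death, graft loss, study withdrawal or documented discontinuation of the prescribed adjunctive drug.
- **Numerator:** days covered by supply within the window, capped at the window length. A single-fill subject is then handled like any other.
- **Threshold:** apply >80% to this value.
- **Alongside it:** report discontinuations of the adjunctive drug by arm, since ending the window there removes them from MPR, and report the drug-count result as a separate measure.

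The cost is one formula. Fill dates and days' supply are already needed for the present formula and counts are already made, so no new data are required. MPR values will be somewhat lower.

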4. Recurrent acute rejection is defined as rejection recurring more than two weeks after documented rejection reversal.
5. Opportunistic Infections will be defined according the American Society of Transplant Recommendations for Screening, Monitoring, and

Reporting of Infectious Complications in Immunosuppression Trials in Recipients of Organ Transplantation (Appendix C1).

5. Treatment of Acute rejection:
 1. Acute rejection will be treated per institutional protocol, listed in Appendix C2.

6. Acceptable contraception methods

Option 1 (monotherapy methods):

1. Intrauterine devices (IUDs)
2. Tubal sterilization
3. Patient's partner had a vasectomy

Option 2 (Choice one from category A AND one from category B):

1. Category A:
 - a. Estrogen and progesterone
 - i. Oral contraceptive pill
 - ii. Transdermal patch
 - iii. Vaginal ring
 - b. Progesterone only
 - i. Injection
 - ii. Implant
 - c. Barrier method
 - i. Diaphragm with spermicide
 - ii. Cervical cap with spermicide
 - iii. Contraceptive sponge
2. Category B:
 - a. Male condom
 - b. Female condom
 - c. Diaphragm with spermicide (for use with hormone therapy)
 - d. Cervical cap with spermicide (for use with hormone therapy)
 - e. Contraceptive sponge (for use with hormone therapy)

7. Intervention Discontinuation Evaluations: At the scheduled time of intervention discontinuation (EOT, last date of study), the following evaluations must be completed: vital signs, clinical assessment, CBC, CHEM-7, Everolimus CO, Tacrolimus CO. In case of subject withdrawal from study, the patient will return to standard of care medications and request to continue with final assessment using MMAS-8, MMSE Scale and SF-36 will be discussed with a qualified team member.

8. Adverse Events

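### The plan promises an intention-to-treat analysis of all subjects but does not require a six-month MMAS-8 from those whose regimen is stopped early

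*Combined protocol and SAP*

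**What the plan says.** The primary outcome is the difference between arms in MMAS-8 change from baseline to six months (Section 10.1). On who is analysed, Section 10.3 states: "Under the intention-to-treat principle, all subjects are included in the analysis". It accepts that some data will probably be missing and promises efforts to limit this. Although its title mentions imputation, it names no method.

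On collection, the plan says the following.

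- **Length of follow-up (Section 4.1).** Subjects are followed for six months "or until a terminal end point is reached". That end point is not defined.
- **Early stopping (Section 9).** "The intervention will be withheld/discontinued for AE of grade 3 or higher or if requested by the study participant". Pregnancy and graft loss are further reasons. The section does not say what is collected afterwards.
- **Scheduled end of treatment (Section 7).** On the last study date "the following evaluations must be completed: vital signs, clinical assessment, CBC, CHEM-7, Everolimus CO, Tacrolimus CO".
- **Withdrawal from the study (Section 7).** The patient goes back to standard of care, and the "request to continue with final assessment using MMAS-8, MMSE Scale and SF-36 will be discussed with a qualified team member".
- **Timing of MMAS-8.** The schedule table in Section 5.1 marks it at baseline and Day 180 only. Section 4.2 says it is used at all study visits in that schedule.

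**The concern.** A subject stopped early under Section 9 fits neither case in Section 7: it is not the scheduled end of treatment, and stopping a drug is not the same as leaving the study. The only text describing a return to standard of care is the withdrawal sentence, so site staff could easily apply it to these subjects. The final MMAS-8 would then be optional and undated. Under the table there is no interim score to fall back on, so one missed visit removes the primary outcome.

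Such losses are plausibly related to outcome, because adverse events and a subject's own request can both reflect how the regimen suits the subject. They may also differ by arm. The trial is open-label. The control arm changes only the tacrolimus product, while the intervention arm also replaces MMF with everolimus and has a different tacrolimus target. Pre-randomisation standard of care is a twice-daily regimen, so an intervention subject who returns to it loses the once-daily feature under test. If that subject's score is not collected, the comparison loses information that an intention-to-treat analysis is meant to keep.

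**Working it through.** **Inputs.** Section 3: "There will be 20 subjects in each arm, with a total study size of 40 subjects". Section 10.2: a between-arm difference of "2 ± 2 points (95% CI 0.73,3.27) with 87% power", and 85% of enrolled subjects expected to complete all visits. Alpha and sidedness are not stated; two-sided 0.05 is assumed because a 95% interval is quoted.

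**Step 1: reproduce the plan's figure.** SE = 2 × √(1/20 + 1/20) = 0.632. The noncentrality is 2 / 0.632 = 3.16 on 38 degrees of freedom, giving t-test power of 86.9%. A t-based interval is 2 ± 2.024 × 0.632 = 0.72 to 3.28, close to the stated one. The 87% therefore assumes an MMAS-8 change score for all 40 subjects.

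**Step 2: how many scores could be lost.** 15% × 40 = 6. This is an upper reading of the plan's figure, since a subject who misses an interim visit is a non-completer but may still attend Day 180.

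**Step 3: power with 34 scores** (difference and SD unchanged).

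- 17 v 17: SE = 2 × √(2/17) = 0.686, power 80.7%.
- 20 v 14: SE = 2 × √(1/20 + 1/14) = 0.697, power 79.5%.

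**Step 4: bias in the between-arm difference.** Let a and b subjects be missing in the two arms, and let each have a change g points worse than completers in the same arm. Each arm's all-subject mean differs from its completer mean by (missing/20) × g, so with the same g in both arms the bias is (a/20 − b/20) × g. The documents give neither arm-specific withdrawal rates nor g. The range g = 2 to 4 is an assumption, equal to 1 to 2 of the plan's SDs.

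| Missing (a v b) | g = 2 | g = 4 | Share of 2-point target |
|---|---|---|---|
| 3 v 3 | 0 | 0 | 0% |
| 4 v 2 | 0.2 | 0.4 | 10–20% |
| 5 v 1 | 0.4 | 0.8 | 20–40% |
| 6 v 0 | 0.6 | 1.2 | 30–60% |

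Equal numbers do not guarantee zero bias. If 3 v 3 are missing but only one arm's missing subjects are worse, the bias is 3/20 × 2 to 4 = 0.3 to 0.6. In every case it favours the arm that loses more poor scores, whichever arm that is.

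**The case against.** The best defence is that the plan's default is continued follow-up. Section 4.1 follows subjects for six months, Section 5 has all subjects assessed on schedule, and Section 10.3 promises efforts against loss. Section 9 stops the intervention, possibly only as a pause, and does not say that follow-up ends. This is also a small pilot: "No formal power analysis conducted since this is a pilot study".

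Much of that stands, and it rules out several stronger readings that a reader might infer.

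- **That subjects who stop the regimen are dropped from follow-up.** The discussed-request sentence concerns withdrawal from the study, and it does provide for asking. For early stopping the plan is silent.
- **That the end-of-treatment list omits MMAS-8.** The list includes the clinical assessment, and in the schedule table the MMAS-8 row sits under that heading and is required at Day 180. However, the next sentence of Section 7 names MMAS-8 separately, so the wording is ambiguous.
- **That a subject who stops has no post-baseline score.** This is true of the table but not of Section 4.2.
- **That the missing subjects will be those doing worst, or that the analysis is completers-only.** Neither is stated. Grade 3 events, pregnancy and graft loss are not poor adherence.
- **That 6 of 40 will lack a Day 180 score.** The 85% concerns all visits.

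The defence does not supply a rule. General intentions to follow everyone do not tell a site to obtain an MMAS-8 at Day 180 from a subject who stopped the regimen at, say, Day 60. Extra visits under Section 4.2 do not provide the six-month value either.

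**Conclusion.** The concern holds as a gap in required data collection. The plan commits to analysing all subjects but has no binding rule that obtains the six-month primary outcome after early stopping, and it leaves the follow-up end point undefined. The outcome may be missing, plausibly not at random and unequally by arm.

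The bias is anywhere from 0 (3 v 3 missing, equal deficits) to 1.2 points (6 v 0, 4-point deficit) on a 2-point target. That range rests on up to six lost scores and an assumed deficit of 2 to 4 points; the upper end is an extreme split, not a forecast. The loss of power, from 87% to about 80%, needs only the six lost scores and a two-sided 0.05 test. The change is worth making even in a pilot because it is cheap, and no later analysis can recover scores that were never collected.

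**What to change.** 1. In Section 7, separate stopping the regimen from withdrawing consent to follow-up, and say what the undefined end point in Section 4.1 means for data collection.
2. Require MMAS-8, with the Memphis scale and SF-36, at Day 180 (by phone if needed) from all randomised subjects who are alive and have not withdrawn consent. Name MMAS-8 explicitly in the Section 7 list.
3. Reconcile the MMAS-8 timing in Section 4.2 with the schedule table.
4. In Section 10.3, state that off-regimen scores enter the intention-to-treat analysis, and say which regimen the questionnaire then refers to. Name the primary missing-data method, and add a sensitivity analysis that gives unfavourable values to scores still missing.

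The cost is protocol wording and a few extra questionnaires. The estimate will describe the effect of being assigned to the regimen, and may look slightly smaller than an effect among completers.
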